3.3.1.2. Pilot Study	10
3.3.1.3. Inclusion Criteria:	10
3.3.1.4. Exclusion Criteria:.....	10
3.3.1.5. Withdrawal Criteria:	11
3.4. Diagnosis	11
3.5. Randomization and Blinding	11
4. Patient information and informed consent to participate:.....	12
5. Confidentiality:	12
6. Clinical Procedures	12
6.1. Endodontic procedures	12
6.2. Post-endodontic pain assessment	13
7. Concomitant Treatments	13
8. Schedule	13
9. Reporting of Unexpected Serious Adverse Events, Serious Adverse Events and Adverse Events	14
10. Premature Termination of the Study.....	15
11. Statistical Analysis.....	15
12. Financing and Insurance	15
12.1. Reimbursement of Patients' Expenses	15

12.2. Insurance for Patients	15
13. Publications policy	15
14. References	15

Comparative evaluation of the effectiveness of root canal preparation after irrigation using endodontic needle and inertial cavitation: A randomized controlled trial

Introduction

Postoperative pain after root canal treatment is a clinical challenge influenced by host-dependent (preoperative pain, occlusal trauma) (Glennon et al. 2004, Yu 2004) and operator-dependent factors (chemical, mechanical or microbiological factors) (Siqueira & Barnett 2004). It is mainly attributed to the extrusion of infected debris into the periapical area. (Siqueira JF 2003). Although the incidence of postoperative pain was reported to be around 40% of cases, it can reach 80% within the first 24 hours after the treatment (Pak & White 2011). While host-dependent factors cannot be influenced, the operator-dependent factors such as instrumentation materials, shaping kinematics, irrigation material and method can be controlled to minimize or avoid postoperative pain (Tanalp and Gungor 2014, Mostafa et al. 2020).

Chemo-mechanical debridement of the root canal system is important to achieve an optimal disinfection and shaping of the root canal and is a prerequisite for a successful treatment outcome (Topcuoglu et al. 2018, Eyuboglu & Özcan 2019). Optimal shaping and disinfection require both mechanical and chemical debridement as large areas of the root canal system were shown to remain untouched even after the completion of root canal shaping (Brito et al. 2009, Howard et al. 2011). The comparison of root canals using micro computed tomography before and after root canal treatment also presented non-prepared areas within the root canal system and shortcomings of mechanical shaping (Peters et al. 2001). Therefore, root canal irrigation, the chemical part of the debridement, plays a key role in optimally disinfecting the root canal system, especially on these untouched areas (Versiani et al. 2016, Estevez et al. 2017). However, there is no single, ideal irrigation solution that can penetrate the entirety of the root canal structure. This is not sufficiently improved by increasing the temperature, lowering pH, or increasing wettability. To this end, new irrigation solutions have been proposed such as combining sodium hypochlorite (NaOCl) with ethylenediaminetetraacetic acid (EDTA) as initial or final irrigation solution (Zehnder 2006).

Endodontic needles with differently shaped tips and designs are the most common way to deliver the irrigation solutions into the root canal system (Boustaoukis et al. 2010). However, irrigation using endodontic needles does not remove all debris especially within the canal extensions at the apical third of the root canal system due to limited fluid penetration (Tay et al. 2010, Chan et al. 2019).

Different devices or methods for agitation or activation of the irrigation solution have been introduced to increase the efficacy of the irrigation solution within the root canal system and thus create optimal disinfection (Gu et al. 2009, Dutner et al. 2012, van der Sluis et al. 2015).

During ultrasonically activated irrigation (UAI) the irrigation solution is activated with a noncutting oscillating tip within the root canal system (Boustaoukis et al. 2013). Acoustic microstreaming, a unidirectional circulation of fluid, is created by UAI. During the acoustic microstreaming, transient (inertial) cavitation was observed (Macedo et al. 2014). Inertial cavitation can only be created under the right physical conditions within the root canal system (Flynn (1975)a, Flynn (1975)b, Birkin et al. 2011). There are several reasons for the disappearance of acoustic microstreaming within the root canal such as airlock formation in the apical third of the canal (de Gregorio et al. 2009, Peeters et al.

2013) or the oscillating tip getting stuck in the apical third thereby obstructing the oscillating movement (Jensen *et al.* 1999).

In order to overcome such problems, a novel medical device "EndoClean" (Lumendo AG, Renens, Switzerland) has been developed that generates hydraulic cavitation to clean root canals deeper and more effectively than other systems described above. This method overcomes the problem of the stagnation plane formation (around 1-2 mm in front of a syringe [Gulabivala *et al.*, 2010]), permitting the irrigation solution to access deeper into the root canal system and thus providing a fast and efficient way of cleaning the root canal.

It is known that extrusion of irrigation solution may damage the periapical tissues and cause postoperative pain (George & Walsh 2008). Although there are data presenting similar amount of irrigation solution extrusion between UAI and manual irrigation (Mitchell *et al.* 2011), no data regarding the short term (postoperative pain) effects of the novel device, EndoClean, is available. For this reason, a pilot clinical study for EndoClean is planned.

Objectives and hypothesis

The primary objective of this randomized controlled trial is to compare the postoperative pain intensity levels in patients with asymptomatic teeth diagnosed for non-surgical orthograde root canal treatment that are disinfected during the root canal treatment procedure by manual irrigation with sodium hypochlorite (NaOCl) solution or EndoClean. The secondary objective is to evaluate, if EndoClean could be used safely during root canal treatment as an alternative approach to manual irrigation. The null hypothesis is that there will not be a significant difference in postoperative pain intensity levels between patients who will undergo root canal treatment with manual irrigation with NaOCl or EndoClean.

STUDY PROTOCOL

The "Clinical Investigation" complies with the requirements of the World Medical Association Declaration of Helsinki (2013) and ISO 14155:2020 (Clinical investigation of medical devices for human subjects - Good Clinical Practice).

1. Sponsor:

Lumendo AG (CHE-165.176.923), [name]
(<https://www.lumendo.ch/>) by its authorized representatives:

CTO:

[name]

[contact]

E-mail: [contact]

CEO:
[name]
Cell: + [contact]
E-mail: [contact]

Clinical Affairs Manager:
[name]
[contact]
E-mail: [contact]

2. Principal Investigator

Name-Surname [name]
Institution: İstanbul Medipol University, Faculty of Dentistry, Department of Endodontics
Address: [name]
[contact]
E-mail: [contact]

3. Preparation of the Investigation:

3.1. Ethical Considerations:

The ethical considerations of the "Clinical Investigation" are based on the Declaration of Helsinki (2013). The approval by the "Ethics Committee" is the prerequisite for the start of the "Clinical Investigation".

3.2. Investigational device

3.2.1. General description of the investigational device

Endoclean generates hydraulic cavitation within the root canal. The cavitation provides a strong erosive effect that allows the removal of bacteria, smear layer, pulp tissue and dental debris based on mechanical action only. Endoclean intends to overcome the disadvantages of chemical irrigation system that either cannot fully reach all parts of the root canal system, is very cumbersome to use and is highly toxic to the surrounding tissue. It further intends to reduce the number and extend of mechanical filing steps, thus firstly reducing the overall treatment time and secondly reducing the complication risk of extensive mechanical filing.

Endoclean is applied following conventional access cavity preparation, pulp removal, glide path preparation and root canal length measurement. The Endoclean tip needs to reach within 3 mm from the apex. Accordingly, in very narrow canals minimal shaping is required. Endoclean is applied for 60 seconds in every root canal in an up-and-down movement.

3.2.2. Traceability and accountability of the investigational device

Traceability will be controlled during and after the investigation period by means of the lot number of the device. Only one device will be used in this study. The lot number of the device used in each finished clinical case will be included in the case report and recorded in a datasheet specifically-designed for that purpose.

The device will be delivered directly to the Site by Lumendo staff. The device will be stored and transported according to the regulations written in the instructions.

After completion of the study the used device will be returned to Lumendo by Lumendo staff or express shipping.

3.2.3. Intended purpose of the investigational device

Endoclean is intended to clean and remove bacteria, smear layer, pulp tissue, and dental debris from the root canal during root canal treatment.

3.2.4. Intended patient's population

Intended patients profile include individuals in need of root canal treatment (endodontic treatment), most commonly due to progressed tooth decay, faulty fillings, or tooth trauma which has resulted in an infection in the pulp and root of the tooth. The patients are otherwise in relatively good health, do not suffer from unrelated acute conditions or diseases and the chronic diseases, if present, are properly managed.

3.3. Study Design and Setting

The protocol of this prospective, 2-arm, randomized controlled clinical trial and consent forms for the patients will be approved by the ministry of health and ethics committee of the university. The study will be registered on www.clinicaltrials.gov. The study will be following the Consolidated Standards of Reporting Trials (CONSORT) guidelines (**Moher et al. 2010**). All patients will be informed about the nature of the study, the treatment procedures, evaluation process, benefits, and the potential risks before they will be asked to sign a written consent form. The enrolment of patients will be executed from the outpatient clinic of Department of Endodontics, Faculty of Dentistry, Istanbul Medipol University, Turkey.

3.3.1. Patient Population:

3.3.1.1. Sample Size Calculation

In order to determine the number of samples, power analysis was performed using the G*Power (v3.1.9.2) program. The power of the study is expressed as $1-\beta$ (β = probability of type II error). Based on the postoperative 6th-hour pain measurements in the article by D. Liapis et al.*, the mean for

Group I was 13.9 SD:16.2; When the mean for Group II was taken as 4.9 SD: 7.3, the effect size (d) was found to be 0.716 in the calculation made to obtain 90% power at the $\alpha=0.05$ level. Accordingly, it was calculated that there should be at least 42 people in each group and 84 people in total. Considering that there may be losses during the study process (20%), it was decided to take at least 50 people in each group.

3.3.1.2. Pilot Study

10 patients will be involved in a pilot study. There will be 5 patients in each group: manual final irrigation and EndoClean device. Pilot study will be conducted for two reasons. The first reason is to ensure the safety of the device for clinical use. Thesecond reason is to conduct an accurate power analysis and therefore, a sample group for the full clinical study. A full clinical investigation will be performed once the pilot study is done, and which will be powered according to the outcome of the pilot study.

3.3.1.3. Inclusion Criteria:

1. Physical status classification system described was used for patients' recruitment. Healthy patients, who were classified by the American Society of Anaesthesiologists (ASA) as ASA I and II
2. Patients with the age of 18 and over
3. Patients who were diagnosed as in need of non-surgical orthograde root canal treatment of an asymptomatic tooth
4. Tooth without signs of previously initiated Root Canal Therapy

3.3.1.4. Exclusion Criteria:

1. Pregnant and lactating females
2. Patients with chronic periodontal diseases
3. Patients with sensitivity or adverse reactions to any medication or materials that were used throughout the treatment procedure
4. Patients with acute periapical periodontitis
5. Patients with acute periodontal abscess
6. Patients who could not abide by the follow-up time
7. Patients who used analgesics 1-week prior or antibiotics 1-month prior to treatment
8. Uncooperative patients
9. Teeth that cannot be made functional nor restored or difficult to access teeth with no importance (wisdom teeth)
10. Teeth with poor prognosis, for example, due to deep root caries or big root resorption
11. Teeth with ≥ 4 mm periodontal pocket depth
12. Teeth with an inaccessible root end
13. Teeth with apical resorption or a radiologically not clearly defined apex
14. Fractured teeth
15. Teeth with immature or open apices
16. Teeth with root apices extending into the maxillary sinus

17. Teeth with external resorption communicating with the pulp

3.3.1.5. Withdrawal Criteria:

Subjects may be withdrawn from the study at the discretion of the Investigator or Sponsor due to a safety concern or if judged non-compliant with trial procedures.

A subject must be withdrawn from treatment if one of the following applies:

- Subject chooses to withdraw from the study at any time;
- Intolerable adverse effects;
- Other circumstances that would endanger the health of the subject if he/she were to continue his/her participation in the trial.

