6.2. Post-endodontic pain assessment

After the treatment, all participants will be provided with analgesics (75 mg diclofenac sodium) (Voltaren SR 75 mg, Novartis, Kurtköy, İstanbul) and will be advised to use them if needs be and record the time of use. A pain intensity evaluation diary including VAS diagrams with their respective follow-up evaluation times will be provided to each participant to mark their pain. All participants will be contacted on their follow-up time to remind them to mark their pain intensity scores. Pain intensity of patients will be evaluated at 6h, 24h, 48h, 72h and 1 week after the completion of root canal treatment as previously described. Any complication such as paraesthesia, acute exacerbations, flare-ups, swellings will be also recorded on patients' charts. Patients who fail to abide by the follow-up time will be traced via phone, e-mail or SMS to determine the possible reasons for dropout.

7. Concomitant Treatments

Medications given to patients are to be documented

8. Schedule

The duration of the investigation and the post-assessment has to be justified.

Study duration:

Step 1. Patients enrollement: 2 months

Step 2. Treatment duration: 1 visit to dentist

Step 3. Follow-up period: 1 week

Flow chart of the study:

Investigation Periods	Consent (ICF) Screening	Treatment	Follow-up				
Visit	1 On-site	2 On-site	3	4	5	6	7 On-site
Time (hour, day, week)	-1 week	0	6 hours	24 hours	48 hours	72 hours	1 week
Patient consent (ICF)	x						
Demographics	x						
Medical History	x						
In- /Exclusion Criteria	x	x					
Dental Examination	x						x
X-ray		x					
Randomization		x					
Medical device application		x					
Concomitant Therapy,	x	x	x	x	x	x	x
(Serious) Adverse Events, Adverse device effects	x	x	x	x	x	x	x
Pain intensity			x	x	x	x	x
Pain intensity diary dispensing		x					
Pain intensity diary collection							x

9. Reporting of Unexpected Serious Adverse Events, Serious Adverse Events and Adverse Events

Unexpected Serious Adverse Events and Serious Adverse Events must be reported to the sponsor within 24 hours after awareness of the event by the Investigator. Unexpected Serious Adverse Events must be reported to the Ethics Committee and Regulatory Authority within identified timeline as per the regulations.

10. Premature Termination of the Study

If excessive pain will be experienced by three concomitant patients the study will be terminated.

11. Statistical Analysis

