4.1 Primary Outcome: All participants will be asked to grade their pain intensity level on a horizontal Visual Analogue Scale (VAS) before the treatment procedure. This scale is a horizontal 100 mm bar, marked in every 10mm with two ends. One end (0) indicated “no pain” and the other end (10) indicated “worst pain possible”. Categorization of pain scores is as follows: 0-4 mm = No Pain, 5-44 mm = Mild Pain, 45-74 mm = Moderate Pain, 75-100 mm = severe pain. After grading the pain level, the distance between the marked point and the “no pain” endpoint will be measured with a ruler to calculate the pain intensity level. Clinical and radiological findings consistent with the asymptomatic tooth with nonvital pulp tissue with the preoperative pain intensity scores in the category of “no pain” will be included in the study.

4.2 Secondary Outcome: If excessive pain will be experienced by three concomitant patients the study will be terminated.

5. Populations to be Analysed

Data of all randomised study subjects will be analysed. This will be seen as the primary population for the analysis. For any specific analysis, study subjects with missing data on any of the variables in the model will be excluded from the analysis.

6. Analyses

All outcomes will be presented using descriptive statistics; normally distributed data by the mean and standard deviation (SD) and skewed distributions by the median and interquartile range (IQR). Binary and categorical variables will be presented using counts and percentages. Python programming language and its dependent statical libraries will be used for all statistical analysis.

The subsections below will describe analyses in addition to the descriptive statistics.

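### Five EndoClean patients cannot ensure device safety, and neither document places a safety decision between the pilot and the full study

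*Protocol*

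**What the plan says.** Protocol 3.3.1.2 sets the pilot's size and split: "10 patients will be involved in a pilot study" and "There will be 5 patients in each group: manual final irrigation and EndoClean device". It gives two purposes. The first concerns safety: "The first reason is to ensure the safety of the device for clinical use". The second is to inform the power analysis. On what comes next it says: "A full clinical investigation will be performed once the pilot study is done, and which will be powered according to the outcome of the pilot". SAP 2.1 carries the same text.

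Other provisions that bear on safety:

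- Protocol section 10 has one rule for the study as a whole: "If excessive pain will be experienced by three concomitant patients the study will be terminated". It gives no VAS threshold, arm or denominator.
- Protocol 3.3.1.5 lets the investigator or sponsor withdraw individual subjects over a safety concern.
- Protocol 6.2 and the section 8 flow chart have complications, adverse events and device effects recorded up to 1 week.
- Protocol section 9 requires serious events to reach the sponsor within 24 hours. Unexpected serious events also go to the ethics committee and the regulator.

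Safety is also a trial objective: "The secondary objective is to evaluate, if EndoClean could be used safely during root canal treatment as an alternative approach to manual irrigation". In the SAP, the entry under secondary outcome is only the termination rule: "4.2 Secondary Outcome: If excessive pain will be experienced by three concomitant patients the study will be terminated".

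**The concern.** The plan claims a property that the pilot's size cannot give it. The introduction to the protocol says that no data on the short-term effects (postoperative pain) of this device are available and gives this as the reason for a pilot, so the pilot carries real weight.

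Two gaps add to the overclaim. First, no acceptable complication rate, go/no-go criterion or review is stated between pilot and full study. Second, the SAP attaches no safety analysis to the secondary objective. SAP 6.1 models pain scores only. The descriptive statistics promised in SAP section 6 apply to outcomes, and complications and adverse events are not named as an outcome.

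At stake are the basis on which further patients are treated with the device and what the final report can say about safe use.

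**Working it through.** **The plan's own figure.** The documents give no precision, event rate or rationale for 5 per group, so there is no pilot safety figure to reproduce. The one sample-size figure they give, for the full study, does reproduce:

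- Pooled SD = √((16.2² + 7.3²)/2) = 12.56.
- d = (13.9 − 4.9)/12.56 = 0.716.
- The exact two-sided t test at α = 0.05 first reaches 90% power at 42 per group (power 0.9002). That matches the 42 stated.

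This calculation concerns mean pain at 6 hours and says nothing about complications.

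**What no events in five would show.** Input: n = 5 device patients (Protocol 3.3.1.2). With 0 events, the exact binomial upper limit is 1 − a^(1/n).

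- One-sided 95%: 1 − 0.05^(1/5) = 0.451, or 45%.
- Two-sided 95%: 1 − 0.025^(1/5) = 0.522, or 52%.

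**How often five patients would miss a real problem.** The documents give no expected complication rate, so the rates below are assumptions. The chance of no event is (1 − p)^5.

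| Assumed true rate | Chance of 0 events in 5 |
|---|---|
| 5% | 0.95^5 = 77% |
| 10% | 0.90^5 = 59% |
| 20% | 0.80^5 = 33% |

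**How many event-free device patients would rule out a given rate** (one-sided 95%). The number is the smallest n ≥ ln(0.05)/ln(1 − p): 14 for 20%, 29 for 10% and 59 for 5%.

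**What the full study could show.** With 0 events, 42 device patients give an upper limit of 6.9% (one-sided) or 8.4% (two-sided). For 50 the limits are 5.8% and 7.1%. Both sizes are provisional, because the full study is to be re-powered from the pilot.

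**The three-patient pain rule during the pilot.** Assume a 20% chance of excessive pain per patient and independence between patients, and read the rule as three or more affected in the pilot.

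- Only the 5 device patients count: P(X ≥ 3) = 10(0.2³)(0.8²) + 5(0.2⁴)(0.8) + 0.2⁵ = 0.0512 + 0.0064 + 0.0003 = 0.058, or 6%.
- All 10 pilot patients count, with the same rate in both arms: P(X ≥ 3) = 1 − [0.8^10 + 10(0.2)(0.8^9) + 45(0.2²)(0.8^8)] = 1 − (0.107 + 0.268 + 0.302) = 0.322, or 32%.

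The wording does not say which reading applies. On either one, the rule covers pain only and not the other complications that Protocol 6.2 records.

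**The case against.** A small first cohort before wider use is a common staged design, and the documents do not leave patients unprotected. A single serious event would reach the sponsor within a day, an unexpected one would also reach the ethics committee and the regulator, and individuals can be withdrawn for safety. A reader might infer that the pain rule is the only thing that could intervene. The documents do not support that. What stands is narrower: these provisions work through reporting or individual patients, or cover pain alone, and none is a decision on whether to go from pilot to full study.

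Other inferences also go too far:

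- **That safety is settled after five uneventful cases.** No section says so, and the safety objective belongs to the trial as a whole.
- **That the full study starts whatever the pilot shows.** "A full clinical investigation will be performed once the pilot study is done" sets no safety condition, but it does not say that safety findings would be ignored.
- **That at least 50 more device patients will be exposed on this basis.** The figure of 50 per group is provisional, and the documents do not say whether pilot patients count toward it.
- **That the pain rule has only a 6% chance of acting at a 20% rate.** This needs a restriction to device patients that the rule does not contain.

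It is also unclear whether the full investigation runs under this protocol. Protocol section 11 describes a pilot with exploratory statistics, while the sample-size section and the SAP read as one study. If a separate protocol is intended, a start decision could sit there.

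Finally, the primary pain comparison and its estimate are unaffected. That limits the weight of the point but does not answer it.

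**Conclusion.** The concern holds in limited form. Five device patients followed for 1 week cannot ensure safety: a complication-free pilot leaves any rate up to 45% (one-sided 95%) or 52% (two-sided) compatible with the data. The text ties the start of the full study to completion of the pilot and the pilot's outcome to powering, with no safety decision in between. The pain rule does not fill that gap. At an assumed 20% rate its chance of acting in the pilot lies between 6% and 32%, depending on a reading that the documents leave open.

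The limits treat patients as independent and count each patient once for any one type of complication. The 5%, 10% and 20% rates are illustrations, not estimates. This should be corrected before the pilot is used to support the next stage.

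**What to change.** Make the same changes in Protocol 3.3.1.2 and SAP 2.1:

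1. Replace the claim to ensure safety with: *to obtain a first look at complications and feasibility; no events in five device patients would exclude only rates above 45% (one-sided 95% limit; 52% two-sided)*.
2. Make the start of the full study depend on a documented review, by sponsor and investigator, of the pilot's 1-week complications and adverse events by arm.
3. State, in SAP 4.2 and section 6 as well, that the secondary safety objective is answered from the full study's complication and adverse event data, by arm, with exact confidence intervals.
4. If the full investigation is to have its own protocol, say so and place the review step there.

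No extra patients or new data are needed. The downside is a weaker stated claim and a pause of about one week for the last pilot patient's follow-up. Part of that wait is already implied, since the full study is to be powered from the pilot's outcome.

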6.1. Endodontic procedures

All treatment procedures will be performed in a single visit by a single treatment provider. It will be assured that the operation room is quiet and isolated throughout the whole process to avoid any outside interference. Patients will be made comfortable and informed about the steps of the procedure a second time right before commencing the treatment protocol. Patients will be also reminded that they will get the necessary treatment even if they decline from the study and should not feel compelled to participate the study for a proper treatment. All root canal treatments will be performed using a dental loupe with a magnification of 4.50X (EyeMag Pro F; Carl Zeiss).

Each tooth will be anaesthetized with 2 mL local anaesthetic solution containing 40 mg/mL articaine hydrochloride and 12 mg/mL epinephrine hydrochloride (Ultracaine DS Forte; Aventis Pharma). After isolating the tooth with a rubber dam (Hygenic Dental Dam Kit; Coltene/Whaledent GmbH & Co.kg, Langenau, Germany) the operation field will be disinfected using 5.25% NaOCl solution (Wizard; Rehber Chemistry) soaked cotton rolls.

After the access cavity preparation, a #10 C-File (MMC file, Coltene-Micro-Méga, Besançon, France) will be introduced into the root canal for scouting. Coronal flaring of root canals will be performed using a nickel-titanium flaring file (One Flare; Coltene-Micro-Méga) with an electric endodontic motor (Dual Move, Coltene-Micromega). Working length determination will be performed with a #10 C-file (MMC file, Coltene-Micro-Méga) and glidepath preparation will be completed with a One G (Coltene-Micro-Méga). The shaping of the root canals will be performed using One Curve (#25/0.06, Coltene-Micro-Méga). If further shaping of the canal will be needed 2 Shape F35 (#35/0.06) (Coltene-Micro-Méga) files will be used according to apical canal lumen. All rotary files will be used according

to the manufacturer's instructions. The filing protocols and files used will be recorded in the patient file.

In Group 1, 2 mL of NaOCl solution will be used after each file as an irrigation solution. After the shaping of the root canal is completed final irrigation with a 31G double side vented tip is performed in each canal using 2.5 mL of 5% EDTA (Wizard; Rehber Chemistry) for 1 minute, 2.5 mL of 5.25% NaOCl for 30 seconds and 5 mL of saline solution for 30 seconds respectively.

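### Protocol 3.3.1.5 does not separate stopping treatment from stopping follow-up, so withdrawal after the single treatment visit can lose later pain scores and later adverse-event follow-up in patients with poor outcomes

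*Protocol*

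**What the plan says.** Protocol 3.3.1.5 (Withdrawal Criteria) contains two rules.

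- **Discretionary, from the study:** "Subjects may be withdrawn from the study at the discretion of the Investigator or Sponsor due to a safety concern". Judged non-compliance is a second ground. No time limit is attached.
- **Mandatory, from treatment:** "A subject must be withdrawn from treatment if one of the following applies". The list below includes "Intolerable adverse effects", but also the subject's own choice to leave the study, and "Other circumstances that would endanger the health of the subject if he/she were to continue his/her participation in the trial".

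On timing, Protocol 6.1 says "All treatment procedures will be performed in a single visit by a single treatment provider", and 6.2 says "Pain intensity of patients will be evaluated at 6h, 24h, 48h, 72h and 1 week after the completion of root canal treatment".

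On patients who miss follow-up, Protocol 6.2 says they "will be traced via phone, e-mail or SMS to determine the possible reasons for dropout". It does not mention obtaining the missing score or asking about adverse events.

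On analysis, SAP 5 takes all randomised subjects as the primary population and then states that "study subjects with missing data on any of the variables in the model will be excluded from the analysis". SAP 6.1 fits repeated pain scores with subject as a random effect and treatment group and visit as fixed effects.

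**The concern.** In a trial with continuing treatment, withdrawal for safety ends exposure. Here exposure ends with the treatment visit. From then on only the pain diary, the adverse-event follow-up and the 1-week examination remain, so withdrawal can only end observation.

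The grounds for withdrawal overlap with what the trial measures: pain is the primary objective and safe use the secondary one. Protocol 3.5 states that neither patient nor operator is blinded, and 3.3.1.5 gives the discretionary decision to the investigator or the sponsor. If patients who do badly are the ones whose observation stops, the missing data depend on outcome and possibly on arm. The comparison of mean pain could then be biased, and the later course of adverse events could go unobserved.

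**Working it through.** **Step 1: what withdrawal can stop, and when.**

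| Period | Study treatment left | Data collection left |
|---|---|---|
| Before or during the treatment visit | yes | yes |
| After the treatment visit, to 1 week | none (6.1) | all five outcome pain scores (6.2); adverse events (section 8 schedule) |

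In the second period the treatment rule has nothing to act on. Site staff must either treat it as empty or read it as leaving the study, and the list's own references to the study and the trial invite the second reading.

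**Step 2: what happens to the data.** No section says that pain scores or adverse events are collected after withdrawal. Tracing asks for reasons only. In SAP 5 the unit excluded is the subject. Read literally, one missing score also removes the scores that a withdrawn patient had already given. Read as applying to missing visits only, the earlier scores stay in the mixed model and only the later ones are lost.

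**Step 3: the plan's own figure.** Inputs from Protocol 3.3.1.1 (6-hour pain): 13.9 (SD 16.2) and 4.9 (SD 7.3).

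- Difference: 13.9 − 4.9 = 9.0 mm.
- d = 9.0 / √((16.2² + 7.3²)/2) = 9.0 / 12.56 = 0.716, as stated.
- A two-sided t-test at 0.05 with 42 per group has power 0.900, so the stated 42 is reproduced.

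**Step 4: possible size (illustration).** The documents give no withdrawal rate. Assumptions: 6-hour pain follows a gamma distribution with the planning means and SDs, the patients with the highest scores are the ones lost, and they are removed as whole subjects.

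- Shape k = (mean/SD)² and scale θ = SD²/mean. 13.9 mm arm: k = 0.736, θ = 18.88. 4.9 mm arm: k = 0.451, θ = 10.88.
- Mean of those below a cutoff c: mean × F(c; k+1, θ) / F(c; k, θ), where F is the gamma distribution function.

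| Patients lost | Mean, 13.9 mm arm | Mean, 4.9 mm arm | Difference | Loss from 9.0 |
|---|---|---|---|---|
| Scores of 75 mm or more (1.0% of the arm), 13.9 mm arm only | 13.10 | 4.90 | 8.20 | 0.8 |
| Worst 2%, 13.9 mm arm only | 12.54 | 4.90 | 7.64 | 1.4 |
| Worst 5%, both arms | 11.25 | 3.64 | 7.61 | 1.4 |
| Worst 5%, 13.9 mm arm only | 11.25 | 4.90 | 6.35 | 2.6 |

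Loss of the worst 5% from the 4.9 mm arm only would instead widen the difference, to 13.9 − 3.64 = 10.26 mm. A lognormal shape for the 13.9 mm arm gives means of 12.34 (2% lost) and 11.18 (5% lost), close to the gamma values.

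**Step 5: the pilot.** Protocol 3.3.1.2 uses 5 patients per group to check safety and to re-power the full study. Under the same gamma for the 13.9 mm arm, losing the single worst of five moves the expected mean from 13.9 to 8.7 mm and the SD from about 16.2 to 8.8 mm. One such loss would matter for the re-powering.

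**The case against.** The case against has substance on several points.

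- **The rules do not force anyone out of the study.** A reader might infer that patients with a safety concern or intolerable effects are automatically removed from the study. The study rule is permissive, and intolerable effects are listed under withdrawal from treatment. This stands. What remains is that the section does not keep the two apart.
- **Safety events are not deleted.** A reader might infer that the worst safety outcomes vanish. The section 8 schedule records adverse events from screening to 1 week, 6.2 puts complications on the charts, and section 9 sends serious events to the sponsor within 24 hours of awareness. The triggering event should be captured. Only its later course can be lost.
- **Earlier pain scores are not necessarily lost.** SAP 5 starts from all randomised subjects, and the mixed model can use partial data. Earlier scores disappear only if the exclusion acts on the whole subject. This stands, and the figures in step 4 assume that it does.
- **The largest figure is a worst case.** The loss of 2.6 mm is 29% of 9.0 mm (2.6/9.0), but it needs loss from one arm only, and the 5% cutoff is 46 mm, just inside the protocol's moderate band (45–74 mm). The inputs are also 6-hour values, while the primary analysis covers five times. This stands.
- **Sponsor access.** Section 5 gives the sponsor access to the capture system, but diaries are collected at 1 week. The documents do not show that anyone deciding on withdrawal sees pain scores during follow-up. Knowledge of allocation and of reported events is enough for the concern, but deliberate selection cannot be inferred.

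None of these points supplies the missing provision for data collection after withdrawal.

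**Conclusion.** The concern holds in a limited form. As written, a withdrawal after the treatment visit can only end data collection. No section provides for pain scores or adverse events after it, and SAP 5 can compound the loss. The result would be missing data related to outcome, in an open-label trial whose withdrawal grounds overlap with its objectives.

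The size cannot be estimated from the documents. The illustrations run from 0.8 mm, through 1.4 mm, to an upper case of 2.6 mm out of 9.0 mm. All rest on the assumed distribution, on the 6-hour planning figures and on whole-subject removal. The 29% loss should not be quoted as an expected effect, and the documents do not support saying that the worst outcomes will leave the data. Confidence is moderate. The change should be made because it is cheap and easiest to make before enrolment.

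**What to change.** 1. **Protocol 3.3.1.5.** Reconcile the *study* and *treatment* wording, and leave clinical safety decisions with the investigator. State that, after the treatment visit, stopping for a safety concern, an adverse effect or non-compliance does not by itself end data collection. Diary VAS scores and adverse events continue to be collected to 1 week unless the patient withdraws consent to follow-up.
2. **Protocol 6.2.** Use the existing tracing contact also to ask the patient to mark the due diary entry and return the diary, and to ask about any adverse event. The VAS is a 100 mm line measured with a ruler, so the contact prompts the marking and cannot replace the measurement.
3. **SAP 5.** State that all collected scores of these patients stay in the primary mixed model, so that one missing visit does not remove the subject.

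The cost is wording in three places and a few more follow-up contacts. Randomisation, treatment procedures and sample size are unchanged.
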